##### **Uncommon Risks**

There is the possibility that the participant may faint during or after the IV insertion procedure.

There is a rare possibility of developing a small blood clot, inflammation, or local infection around the vein where the catheter is inserted. In rare cases, a generalized infection can spread through the bloodstream as a result of the IV catheter.

There may be some side effects from the use of heparin, such as bleeding or allergy. The amount of heparin used is much less than what would be used therapeutically to prevent clotting.

#### *Risks of PSG collection.*

##### **Common Risks**

There may be a minor skin rash or reaction (contact dermatitis) at the sites where the electrodes are placed in response to the conducting gel, the collodion used to adhere the electrodes to the hair, or to the sterile tape used to hold the electrodes to skin on the face.

#### *Risks of insulin-modified IVGTT.*

##### **Common Risks**

There is a second IV inserted for the IVGTT, and the same risks apply to it as to the sampling IV described above.

During the IVGTT, the sampling IV line is placed in a hand/wrist vein and this hand may be placed in a heated box to allow for easier sampling (140 degrees Fahrenheit). This may cause sweating and slight swelling of the hand, and before the IVGTT procedure begins the subject will need to take off any rings that he/she normally wears on fingers of the hand being used. The temperature of the heated box and the subject's hand will be closely monitored throughout the entire IVGTT procedure. The subject is free to remove the hand from this box if there is discomfort during the procedure.

##### **Uncommon Risks**

Intravenous glucose infusion will raise blood glucose levels mildly. There is a rare risk of tissue extravasation if glucose is pushed too quickly through a peripheral IV line. Accordingly, the current IVGTT protocol used on the CCI requires a slow IV push method by an experienced provider who will monitor for pain/tenderness at the infusion site. A specially trained clinician will perform the IVGTT, which have been performed over 100 times in healthy individuals by our research core.

Insulin is injected intravenously in a quantity related to body weight. Insulin lowers blood glucose and can cause a lowering of circulating potassium levels. In lowering glucose levels, there is risk of hypoglycemia. Symptoms of hypoglycemia are reversed rapidly with correction by either oral or IV glucose administration. The IVGTT will be carried out by a specially-trained clinician, and a second nurse will be present throughout the procedure. A symptom check is performed at 30, 60, 120, and 180 minutes after glucose infusion. Blood glucose safety checks are performed 20 minutes before the start of the procedure, as well as 160 min and 180 min after glucose infusion. An “Emergency Medication Kit” is ordered at bedside for each IVGTT that consists of: glucose tablets, IV glucose, IM glucagon, IM epinephrine, IV diphenhydramine, IV hydrocortisone, and acetaminophen. A CCI Standard Operating Procedure dictates threshold values for glucose and corresponding treatment options.

The dose of insulin used in this procedure is small and would not be expected to lead to low potassium levels. As a precaution, the participant's potassium level will be checked to ensure it is within normal range.

#### Radiation risks

Body composition measurement involves radiation exposure from a scan of the whole body using dual x-ray absorptiometry or DXA. The radiation exposure from these scans is less than 1% of the normal, annual background radiation exposure. The risk from radiation exposure of this magnitude is too small to be detected in this study's population.

#### Risks of receiving study visit reminders by text message

Text messages are not encrypted, and thus there is a risk of a loss of privacy. To minimize this risk, we will adhere to the principles of minimum necessary; thus, study-initiated text messages will not contain participant names or other identifiers, sensitive information that could expose financial risk to individuals (social security numbers, driver license numbers, credit card numbers, etc), results of any clinical tests conducted for the purpose of research, or potentially sensitive information about the study visit. Additionally, participants who consent to receiving text messages will first be sent a welcome message by text that requests the participant to respond “yes” to indicate their preference to continue to receive research texts.

#### Other Study Risks.

##### Common Risks

Staff in the CCI metabolic kitchen will calculate a menu cycle based on the individual participant's preferences that meets the diet order and is designed to maintain each participant's weight and adhere to the planned macronutrient content. The participant will be required to eat all the foods they are served at each meal. Furthermore, on each of the occasions that a Mixed Meal Response test is given, the content of that breakfast, and the food on all the meals on the prior day, will be exactly the same. The participant may find this to be unappealing, but they will be consuming foods from a menu of study-compatible options that they choose.

For all scheduled sleep episodes, and for the 2.5 hours before and after each restricted sleep episode in the Sleep Restriction without ALAN condition, the participant will be restricted to bed and will not be allowed to get out of bed. During scheduled sleep episodes, the room will be completely dark. The participant will not be allowed to leave the bed or turn on the lights during the scheduled sleep episodes, even if they find it difficult to remain asleep. They will have to use a bedpan or urinal as needed during this time.

For the assessment of Resting Energy Expenditure and the Mixed Meal Response baseline tests, the participant will be restricted to sitting quietly in bed from the time that they are awakened until the blood sampling from the Mixed Meal test is complete approximately 4 hours later. For the same tests carried out at the end of each sleep restriction intervention condition, participants will awaken 2.5 hours before usual, and thus will remain sitting in bed for approximately 6.5 hours. The participant will have to use a bedpan or urinal as needed during this time.

For the 2.5 hours before and after each restricted sleep episode in the Sleep Restriction without Extended Duration ALAN condition, the lighting in the room will be very dim. This will make it difficult for the participant to

read or do other visual tasks. There will be a trained staff member in the room with them to converse, play a board game, etc.

There will be times when the participants will feel extremely sleepy. There are no known permanent adverse effects from chronic sleep restriction for a limited time such as the 2 weeks in the proposed studies. The participant may experience headache, nausea, upset stomach, or feel very irritable or frustrated when they are very sleepy and not allowed to go to sleep. The participant will be informed that they may withdraw from the study at any point that they feel this sleepiness is too extreme, but they will be required to sleep for at least 4 hours before being discharged from the study.

The assessment of resting metabolic rate will take approximately 20-30 minutes, during which time the participant will be asked to sit underneath a ventilated hood. This may be unpleasant for some individuals. If the subject/patient feels that the discomfort is excessive he/she can choose to terminate the study.

Body composition measurement will be done by a scan of the whole body using dual x-ray absorptiometry or DXA. This may involve the minor discomfort of lying still for 5 minutes.

Mild discomfort may occur when the continuous glucose monitor sensor is first placed. It should not be uncomfortable while wearing it. Mild skin irritation may occur when the sensor is removed at the end of the sampling segment.

Mild irritations such as edema, rash, bleeding, itching and infection may occur from the site where the continuous glucose monitor sensor is placed. In our study, the sensor will be placed by a nurse after cleaning the skin in order to minimize the risk of infection. The site will be checked daily by a CCI nurse and the placement moved if edema, rash, itching, or bleeding occurs.

Participants may feel uncomfortable answering some of the questions that are part of the pre-study screening process.

Participants may feel uncomfortable answering some of the questions that are part of the hospital admission process.

Participants may feel uncomfortable viewing the emotional imagery used in some of the performance tests.

Participants may feel uncomfortable having a staff member in their room throughout the entire wake episodes during the week of sleep intervention. They will be informed of this monitoring ahead of time, and can choose to end the study early if they feel they cannot tolerate it.

Because of the sleep loss experienced during the study, participants will be advised that they will likely be sleepier than usual after the study is complete, and that this may last for several days. They will be advised to allow themselves extra time for sleep and to avoid situations that put them at risk for an accident, such as driving an automobile or operating heavy machinery.

In order to minimize the risks associated with jet-lag type symptoms, participants will be counseled prior to discharge on how to readjust to their regular sleep-wake cycle if they should experience jet lag symptoms. In our experience, most potential participants have either experienced jet-lag in the past, and/or have kept an irregular schedule in the past, and thus can anticipate what these symptoms will be like.

**VIII. Potential Benefits.** Although there will be no direct physical benefit to the participant resulting from participation in this study, we will make known to the participant, upon conclusion of the protocol and analysis of the data, some of the information we have gathered from the physiological testing. This information may help the participant develop a more compatible daily schedule for sleeping, which in turn may result in improved well-being. We will also provide the participant with copies of the screening blood and urine tests, ECG, and physical examination form if they request them.

There is a chance that the pre-study screening will reveal some medical abnormality. This information will be conveyed to the participant at once, together with a recommendation of a local clinic or physician from whom to seek treatment.

The research has the potential to benefit society more widely. This study is designed to evaluate the extent to which circadian disruption induced by longer exposure to artificial light at night contributes to the impairment of glucose metabolism associated with sleep restriction. By the end of the 20th century, Americans were sleeping on average 2 hours less per night than they were at the beginning of the 20th century. In fact, recent polls conducted by the National Sleep Foundation indicate that young and older adults alike report sleeping less than what is recommended [127, 128]. More than a third of adults report sleeping less than 7 hours per night, with

approximately 15% of adults reporting less than 6 hours of sleep per night on a regular basis. While sleep researchers have begun to understand the consequences of acute sleep loss on alertness and performance, far less is understood about the consequences of chronic insufficient sleep [129] or how to mitigate those impacts. While the adverse metabolic consequences of chronic sleep insufficiency are now widely appreciated, the role played by light exposure at night on those metabolic changes is not understood. **By understanding the contribution of extended light exposure on the adverse metabolic changes associated with chronic sleep restriction, we can design and test strategies to minimize or eliminate those risks.**

Experimental studies have demonstrated that chronic sleep restriction impairs glucose metabolism, consistent with epidemiologic studies that show strong links between short sleep, metabolic syndrome, and diabetes. However, less is known about whether one of the mechanism(s) by which insufficient sleep impairs glucose metabolism is light exposure at night. Given that sleep restriction is typically accompanied by longer exposure to artificial light at night, which is known to disrupt circadian rhythmicity, we plan to evaluate the extent to which circadian disruption induced by exposure to extended duration artificial light at night contributes to the impairment of glucose metabolism associated with sleep restriction. **This knowledge can be used to design and test countermeasures and mitigation strategies to minimize the adverse metabolic consequences of chronic sleep restriction.**

## **IX. Monitoring and quality assurance**

**Overall Framework for Safety Monitoring.** This study will be conducted under the regulations and oversight of the Mass General Brigham (MGB, formerly Partners HealthCare System) Human Subjects Committee, required for all studies carried out at the Brigham and Women's Hospital. The PI ([name]) will be responsible for ensuring all Human Subjects regulations and policies are followed, and for reporting to the Human Subjects Committee, as required. Furthermore, the study must be approved by the Harvard Catalyst Clinical and Translational Science Center Scientific Advisory Committee before it can be conducted on the BWH CCI. All study personnel involved in the participant recruitment, study execution, data collection, and data analysis at BWH have completed Human Subjects training as well as training in the procedures required by HIPAA, and must annually certify that they will comply with all such regulations. Drs. [name], [name], [name], [name], [name], [name], [name], and [name] have completed additional training in Medical Ethics as required by their appointments at the Harvard Medical School.

**Individual(s) or Group Responsible for Monitoring.** The PI will be responsible for carrying out the DSMP. Data and safety will be monitored by the PI, with assistance from the study personnel, attending physicians, and CCI nurses, and reported to the IRB as required. The procedures proposed in this study have been in use in the PI's research program for the past 40 years, and his team as well as the CCI research nurses and technicians have used the same procedures in hundreds of studies over the two decades since the CCI-IPM opened.

**Information to be Monitored.** The following aspects of the study will be monitored: enrolment, including accrual and retention and tracking by sex and race/ethnicity; protocol non-compliance; data completeness; and adverse events.

Specific issues to be monitored include: adherence to the sleep schedule, meal diary, and wearing of the actigraphy monitor in the pre-study phase; collection of the blood samples and compliance with the conditions for circadian analysis; conduct of the Mixed Meal response procedure including collection of the frequent blood samples; conduct of the intravenous glucose tolerance tests including collection of the frequent blood samples, and occurrences of hypoglycemia; collection of the PSG data each night of the inpatient study; collection of EEG and EOG data during the wake episodes to verify wakefulness throughout all scheduled times; collection of vigilance and subjective sleepiness data during the scheduled wake times; collection of voice recordings during scheduled wake times, including suitable volume and clarity for proposed audio analyses, enough sentence completeness, and the correct file format (WAV) and storage location; common and uncommon risks as described elsewhere.

**Procedures for Monitoring and Frequency of Review.** During the inpatient study conducted on the CCI, participants will be supervised by CCI nursing staff and technical laboratory personnel to monitor participant Detailed Protocol, version 11

safety. The CCI nursing staff will make daily evaluations of the participant's general health and tolerance of the study protocol, and will insert and maintain the blood sampling IV lines following CCI SOPs. A nurse or physician will insert the continuous glucose monitor probe. A specially-trained CCI nurse and a nurse practitioner will be present throughout the intravenous glucose tolerance tests. A physician will perform an admission physical examination, will review medical and safety data on a daily basis during the inpatient study, and will be available on-call to handle any medical emergency that might arise.

A study team member (postdoctoral fellow) will meet with the participant each day to review their study experience; she will meet with the CCI staff to review their impressions of study progress; and she will review all data collection for timeliness, completeness, and accurate documentation. Moreover, [name] and the postdoctoral fellow on the study team will also be on-call throughout the study to answer questions from CCI staff. Much of the data (PSG, waking EEG, blood sample times, saliva sample times, lights out and lights on times, subjective alertness assessments, voice data) are collected by an integrated data collection system that time stamps each piece of information, puts it into a secure database according to participant code, and is backed up automatically at least daily. Other study data (diet content, assay results, demographic information, REE results) are entered into a secure database using Standard Operating Procedures and double-checked for quality control.

Ongoing study progress will be reviewed weekly by the study team. During these meetings, the Principal Investigator and other members of the research team are present. At these meetings, protocol deviations and incomplete data are reviewed, and decisions are made regarding inclusion/exclusion and individual participant termination; such decisions (individual participant termination) that need to be considered in between the study team weekly meetings are made via conference call.

If required by the NIH, the PI will submit an annual progress report that confirms adherence to the DSMP, including a summary of any data and safety monitoring issues that occurred since the previous reporting period; and describing any changes in the research protocol or the DSMP that may or does affect risk. He will also provide the NIH with all new and continuing IRB approvals during the course of the project if requested.

**How Participant Confidentiality will be Protected.** We and the BWH CCI have multiple steps to protect participant confidentiality. The MGB Human Research Committee requires investigators of NIH-funded human research studies to use a special Certificate of Confidentiality Research Consent Form.

**Safety Monitoring.** A Safety Officer will be appointed for the study. We will select a licensed physician from outside the Division of Sleep and Circadian Disorders as the Safety Officer to avoid any potential conflict of interest. The Safety Officer's CV will be provided to the NIDDK Program Officer prior to appointment for their review.

**Process by which Adverse Events (AEs), including Serious Adverse Events (SAEs and Unanticipated Problems (UPs), will be Managed and Reported.** [name] will make the final determination related to any Adverse Events for reporting purposes, including the severity of any event, nature of the event, and relationship of the event to study procedures, taking information from the CCI nursing staff and any other medical personnel present during an event (such as the specially trained nurses present during the IVGTT procedures) and available data and documentation related to the event. Using this information, the PI will then follow IRB, NIH, and NIDDK guidelines for reporting the adverse event.

**Timeline for Reporting Serious Adverse Events (SAEs and Unanticipated Problems (UPs).** Any adverse event will be reported to the IRB as required within the time frame required to do so (typically 5 working days; serious or unexpected adverse events (AEs) will be reported immediately). The IRB in turn will work with the PI to report the serious adverse events (SAEs) to the NIH Program Officer. Any action by the IRB or the CCI that results in temporary or permanent suspension of the study will be reported immediately to the NIH Program Officer. Minor deviations and non-serious AEs are reported to the IRB annually as part of the protocol continuing review process.

Screening Laboratory Tests and Acceptable Ranges				
	Description	Normal Values	Acceptable Values	Comments
Comprehensive Metabolic Panel				SST, 8.5mL
Glucose (Random)	Serum Glucose	54-118mg/dl	54-150mg/dl	Non-fasting. If >150 mg/dl then repeat fasting
Glucose (Fasting)	Serum Glucose	54-118mg/dl	54-125 mg/dl	
Urea	BUN	9-25 mg/dl	6-50 mg/dl	
Creatinine	Serum Creatinine	0.7-1.3 mg/dl	0.4-1.4mg/dl	
Sodium	Serum Sodium	136-142 mmol/L	3.5-5.0 mmol/L	
Potassium	Serum Potassium	3.5-5.0 mmol/L	3.5-5.0 mmol/L	
Chloride	Serum Chloride	98-108 mmol/L	94-114 mmol/L	
Total CO2	Serum Total CO2	23-32 mmol/L	22-36 mmol/L	
Anion Gap		3-15 mmol/L	2-16 mmol/L	
ALT/GPT	Liver Enzyme	7-52 U/L	5-60 U/L	
AST/GOT	Liver Enzyme	9-30 U/L	5-40 U/L	
Alk Phos	Liver Enzyme	36-118 U/L	20-135 U/L	
Total Bili	Liver Function	0.2-1.2 mg/dl	0.0-1.9 mg/dl	1.2-1.9 mg/dl acceptable as long as other LFTs are WNL
Total Protein	Serum Protein	6.0-8.0 g/dl	5-8.5 g/dl	
Albumin	Serum Protein	3.7-5.4 g/dl	3.5-5.9 g/dl	
Globulin	Serum Protein	2.0-4.0 g/dl	1.6-4.1 g/dl	
Calcium	Serum Calcium	8.8-10.5 mg/dl	8.7-10.5 mg/dl	
Complete Blood Count with Differential				EDTA, 3mL
WBC	White Blood Cells	4-10 K/uL	3-10.5 K/uL	
RBC	Red Blood Cells	3.9-6.0M.uL	3.0-7.0M/uL	
HCT (women)	Hematocrit	36-48 g/dl	34-48 g/dl	
HCT (men)	Hematocrit	38-49 g/dl	36.5-49 g/dl	
HGB (women)	Hemoglobin	11.5-16.4 g/dl	11.0-16.4 g/dl	
HGB (men)	Hemoglobin	12.5-16.6 g/dl	12.0-16.6 g/dl	
MCV	Blood MC volume	80-95 um3	76-100 um3	
MCH	Blood MCH	27-32 uug	24-36 uug	
MCHC	Blood Index	32-36 g/dl	30-38 g/dl	
RDW	Blood Index	10-14.5	9-15.5	
PLT	Platelets	150-450 K/uL	140-500 K/uL	
Lymph %	Lymphocyte %	18-41	10-60%	
Mono %	Monocyte %	2.5-8.5	1.8-14	
Neut %	Neutrocyte %	48-76	32-84	
EOS %	Eosinophil %	0-5	0-9	
Baso %	Basophil %	0-2.5	0-9	
Lymph #	Lymphocyte Absolute	0.8-4.1 K/uL	0.4-5.8 K/uL	
Mono #	Monocyte Absolute	0.10-0.80 /uL	0.02-1.4 K/uL	
Neut #	Neutrocyte Absolute	3.9-7.6 K/uL	2.9-9.0 K/uL	
Eos #	Eosinophil Absolute	0.0-0.5 K/uL	0.0-0.6 K/uL	
Baso #	Basophil Absolute	0.0-0.15 K/uL	0.0-0.3 K/uL	
TSH	Thyroid Stim Hormone	0.5-5.0	0.5-5.0	SST, 3.5mL
Urinalysis				
COLOR		clear/yellow	clear/yellow/amber/cloudy	
SP GR	Specific Gravity	1.003-1.035	1.003-1.045	
PH	pH	4.5-8.0	4.3-8.5	
PRO	Protein	Negative	1+	
KET	Ketone	Negative	1+	
BILI	Bilirubin	Negative	trace	
BLOOD	Blood	Neative	negative (Males) 1+ (Females)	
LEUK	Leukocyte	Negative	No more than one	
ES	Esterase	Negative	of these may be	
NIT	Nitrates	Negative	positive	
URO	urobilinogen	0.2-1.0	0.2-1.2	
WBC	white blood cells	0-4/hpf	<10	
RBC	red blood cells	0-2/hpf	0-2 (males) <10 (females)	
BACT	bacteria	negative	1+ (unless sq epithelial cells present)	
SQ EPI	squamous epithelial cells	variable	variable	
Drug Screen				
Comprehensive Drug Analysis (Urine)	Negative	Negative	If positive for THC, test may be repeated once	
Pregnancy Test (Urine)	Negative	Negative		
Nicotine Metabolite	Negative	Negative		
Alcohol/ETG	Negative	Negative		
Detailed Protocol, version 11	Negative	Negative		
Caffeine	Negative	Negative		
May 28, 2023				
Test results that fall outside the "Acceptable" range can be repeated once to confirm findings

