#### **Inclusion/exclusion criteria.**

**(a) Medication/drug use.** Potential participants must report no history of drug or alcohol dependency. Potential participants must report moderate or no use of caffeine, cigarettes and alcohol by history; be willing to abstain from caffeine, nicotine, alcohol and herbal medications for the duration of the ambulatory segment of the study; and will not be allowed to use these substances during the laboratory segment of the study. Potential participants who are regularly taking any prescription (with the exception for hormonal birth control; see Inclusion of Women and Minorities section) or over-the-counter medication will be excluded.

**(b) Evaluation of medical suitability.** Potential participants must be ambulatory and have no major visual or auditory handicaps. Participants must be free from any acute or debilitating medical conditions. Medical suitability will be determined by clinical history, physical examination, electrocardiogram, clinical biochemical screening tests of blood and urine.

Any participant with symptoms of acute or active illness (e.g., fever, leukocytosis, hypertension) will be excluded from study until those symptoms resolve. Given the wide range of illnesses that are encountered in medical practice, it would not be possible to provide a comprehensive list of each and every disease that could serve as grounds for exclusion for the participant. However, the following summarizes common medical conditions that will be exclusionary.

*Diseases of the Cardiovascular System:* hypertension (systolic blood pressure >130 or diastolic blood pressure >80), heart failure, cardiomyopathy, cor pulmonale, ischemic heart disease, valvular heart disease, history of heart transplantation, cardiac tumors, pericardial disease;

*Disorders of the Respiratory System:* asthma, cystic fibrosis, chronic bronchitis, emphysema and airway obstruction, interstitial lung diseases, pulmonary hypertension, lung neoplasms, ARDS;

*Disorders of the Kidney and Urinary Tract:* acute or chronic renal failure, history of renal transplantation, tubulointerstitial diseases of the kidney, urinary tract obstruction, tumors of the urinary tract;

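### The acceptable serum sodium range in the screening table repeats the potassium range, so no usable sodium limit is stated outside 136-142 mmol/L

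*Combined protocol and SAP*

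**What the plan says.** The protocol ends with a table of screening laboratory tests that has a normal column and an acceptable column. In the metabolic panel the sodium row reads "Sodium Serum Sodium 136-142 mmol/L 3.5-5.0 mmol/L", and its comments cell is empty. The row directly below reads "Potassium Serum Potassium 3.5-5.0 mmol/L 3.5-5.0 mmol/L". The row above sodium is "Creatinine Serum Creatinine 0.7-1.3 mg/dl 0.4-1.4mg/dl" and the row below potassium is "Chloride Serum Chloride 98-108 mmol/L 94-114 mmol/L".

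Two other places give the acceptable column its function. Section III, Inclusion/exclusion criteria, item (b), states: "Medical suitability will be determined by clinical history, physical examination, electrocardiogram, clinical biochemical screening tests of blood and urine". The note under the table says that results outside the acceptable "range can be repeated once to confirm findings".

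No other serum sodium limit is given. The Diet paragraph in Section V sets a sodium intake, and the biomarker panel in the same section lists electrolytes as a possible assay without limits.

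**The concern.** An acceptable range for screening should contain the normal range, and for sodium it lies wholly outside it. The cell is a working threshold, because the repeat rule refers to the acceptable column and the blood tests feed the judgement of medical suitability.

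Followed as written, every candidate with normal sodium is out of range and falls under the repeat rule. Staff who notice the slip and use the normal range have no stated rule for a candidate at, say, 135 or 143 mmol/L. Up to 100 people are expected to enter screening (Section III), and two screeners could reasonably treat the same result differently.

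**Working it through.** **Inputs.** All ranges come from the screening laboratory table. Sodium: normal 136-142, acceptable 3.5-5.0 mmol/L. Potassium: 3.5-5.0 mmol/L in both columns. Chloride: acceptable 94-114 mmol/L. Total CO2: acceptable 22-36 mmol/L. Anion gap: acceptable 2-16 mmol/L.

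**1. Overlap within the sodium row.** The acceptable maximum is 5.0 and the normal minimum is 136. The gap is 136 − 5.0 = 131 mmol/L, so the two ranges share no value.

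**2. Displaced cell or wrong cell?** Creatinine above, and potassium and chloride below, each carry a full and plausible pair of ranges. A shifted cell should leave a neighbour short or misplaced, and none is. The sodium entry equals the potassium entry exactly, which points to copying.

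**3. Is this a convention of the table?** The test is: acceptable low ≤ normal low, and acceptable high ≥ normal high. It applies to the 39 blood rows that print both ranges (17 metabolic panel, 21 blood count, 1 TSH).

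| Reading | Metabolic | Blood count | TSH | Rows that pass |
|---|---|---|---|---|
| Numerals only | 16 of 17 | 21 of 21 | 1 of 1 | 38 of 39 |
| Units as printed | 16 of 17 | 20 of 21 | 1 of 1 | 37 of 39 |

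On numerals, sodium is the only failure. With units as printed, the absolute monocyte row also fails: "Mono # Monocyte Absolute 0.10-0.80 /uL 0.02-1.4 K/uL". There, 0.02-1.4 K/uL is 20-1400 /uL, which misses 0.10-0.80 /uL. The table settles that case itself, because the other four absolute counts use K/uL in both columns, for example "Lymph # Lymphocyte Absolute 0.8-4.1 K/uL 0.4-5.8 K/uL". With K/uL throughout, 0.02 ≤ 0.10 and 1.4 ≥ 0.80, so the row passes. The units-as-printed count treats the full stop in the RBC unit as punctuation, and reads the lymphocyte percentage row, which prints a percent sign in one column only, as a percentage in both.

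**4. Can the intended sodium limit be recovered?**

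- A slipped decimal does not explain it. Multiplying 3.5-5.0 by 10, 100 and 1000 gives 35-50, 350-500 and 3500-5000, and none overlaps 136-142.
- The anion gap row does not pin it down. Assume the usual definition, gap = sodium − chloride − total CO2, which the document does not state. Then sodium = gap + chloride + total CO2, from 2 + 94 + 22 = 118 to 16 + 114 + 36 = 166 mmol/L. That is too wide to serve as a limit.
- The printed cell also conflicts with that row. With sodium at 3.5-5.0, the gap would run from 3.5 − 114 − 36 = −146.5 to 5.0 − 94 − 22 = −111 mmol/L, against an acceptable 2-16.
- The other rows do not show whether a margin was meant. Of the remaining 38, potassium and TSH repeat the normal range exactly and the other 36 are wider on at least one side.

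**The case against.** The strongest reply is that the practical effect is close to nil. The same row prints a usable reference of 136-142 mmol/L, and trained staff would not apply 3.5-5.0 to sodium. The repeat rule is permissive and excludes nobody by itself. Suitability rests on history, examination and ECG as well as laboratory tests, and the study team reviews inclusion and exclusion decisions weekly (Section IX). Sodium is not an outcome, a covariate or a stopping criterion. All of this stands. It fixes the weight of the point at minor, but it does not supply the missing limit.

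A second reply is that the cell could be an artefact of reading the PDF, since a page footer does appear among the drug-screen rows of the same table. That footer belongs to a page break, whereas the sodium row sits mid-table between intact rows. An artefact is unlikely, though only a look at the printed page would exclude it.

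A third reply is that the monocyte unit is a separate slip, and that other cosmetic unit slips exist, such as hematocrit printed in g/dl. That is fair. The monocyte row is included only because it surfaced in the same check and can be corrected at the same time. The sodium conclusion does not depend on it.

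**Conclusion.** The concern holds. The acceptable sodium cell is wrong as written: it is incompatible with the normal range in its own row, identical to the potassium cell, and not recoverable from anything else in the document. Sodium is the one row in 39 that fails on numerals.

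The severity is minor. The consequence is a missing rule for sodium values just outside 136-142 mmol/L at screening. The document does not say how many candidates have such values, so no headcount can be given. Nothing shows a wrong enrolment or exclusion, and sample size, power, analysis and conclusions are unaffected.

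The verdict assumes that the table text matches the printed page. The anion gap definition matters only to the attempt to recover the limit.

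**What to change.** Check the cell against the source page, then replace the acceptable sodium entry with the intended limits. They must contain 136-142 mmol/L. If no margin is intended, print 136-142 mmol/L in both columns, as the potassium and TSH rows already do with their own ranges. Only the sponsor can say which was meant. In the same edit, change the unit of the normal absolute monocyte range from /uL to K/uL.

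The cost is two table cells in the next amendment, with no change to design, procedures or analysis.
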